3.1.1. Dose Modification

Not applicable

3.1.2. Safety Considerations

Aspirin is a well-established medication used routinely in a variety of clinical contexts. It is FDA-approved for use as an antipyretic, anti-inflammatory, and analgesic medication as well as for use following certain revascularization procedures (cardiac stent placement, e.g.). Low dose aspirin also has several off-label uses, including for primary prevention of atherosclerotic disease, preeclampsia prevention, and for thromboprophylaxis. Specifically, aspirin was found to be noninferior to other forms of anticoagulation for postoperative thromboprophylaxis following total hip and total knee replacement.[12] Aspirin is also approved for thromboprophylaxis among low risk patients with multiple myeloma receiving thalidomide-based chemotherapy and/or dexamethasone.[13]

Since aspirin is already widely used among many different patient populations, the risks and side effects are well-established and primarily include medication intolerance, gastrointestinal complications, and adverse bleeding events. Data regarding bleeding events in the setting of limited duration low dose aspirin use for thromboprophylaxis are reassuring. In a retrospective study of low dose aspirin use for postoperative VTE prevention following total hip arthroplasty, the 90-day bleeding rate was 0.52%. [14] Similarly, a systematic review of low dose aspirin thromboprophylaxis after total hip and knee replacements reported no significant difference in cumulative adverse events between low dose aspirin and other anticoagulants; the event rate for major bleeding among patients receiving aspirin was 0.5% with a significant reduction in the incidence of bruising. [12]

Patients receiving chemotherapy are already closely monitored in the outpatient setting with history, physical examination, and lab evaluations prior to every NACT cycle. At each subsequent clinic visit for consideration of an additional NACT cycle, a member of the research team will review medication adherence diaries and AE symptom questionnaires. If symptoms are concerning for a potential AE, the research team personnel will inquire further and discuss with the PI. Please see subsequent sections related to AE monitoring and reporting. No additional components of history and physical exam will be completed outside standard of care performed by the patient's provider prior to initiation of an additional cycle of NACT. Different patients may receive different numbers of cycles, and thus the 30-day supply of aspirin will be re-filled when the decision is made to proceed with an additional cycle.

Any patient with medication intolerance or clinically significant bleeding will be withdrawn from the study to minimize harm. Patients who experience chemotherapy-related thrombocytopenia with platelet count less than 50,000 will be monitored and asked to hold aspirin prophylaxis for 1 week until platelet counts normalize. A designated member of the research team will perform a cumulative review of

adverse events every 3 months and determine if adverse event rates are greater than expected in this patient population.

Performing a pilot study to determine the efficacy and safety of low dose aspirin for thromboprophylaxis when compared with a historical control will help delineate the feasibility of larger studies in the future. This approach mitigates risk while also exploring the potential benefits for patients and the healthcare system overall.

3.1.3. Missed Doses

Subjects will be asked to complete a medication adherence diary, but study analysis will occur in an intention-to-treat fashion. Thus there will be no consequences or alternative regimens for missed doses.

3.1.4. Concomitant Medications/Therapies

Patients who are already on anticoagulation or an alternative (non-aspirin) antiplatelet agent for a specific indication (e.g., cardiac stent) will be excluded from this study. Subjects will be encouraged to disclose any other medications or supplements to their primary provider to be reviewed for interactions with the study drug. Standard of care chemotherapy will not be altered in any way by this investigation. If subjects are already on low dose aspirin for an alternative indication, they will still be eligible for the study but will be instructed to take the study drug such that adherence can be monitored.

3.1.5. Study Drug Blinding

Not applicable

3.1.6. Randomization

Not applicable.

7.2 Rationale for Selection of Dose, Regimen, and Treatment Duration

As previously described, aspirin is approved by the Food and Drug Administration for use as an antipyretic, anti-inflammatory, analgesic, and antiplatelet medication. It is also used off-label for postoperative thromboprophylaxis following total hip and total knee replacement and for thromboprophylaxis among low risk patients with multiple myeloma receiving thalidomide-based chemotherapy and/or dexamethasone. The dosing, regimen, and treatment duration were established in accordance with the guidelines for the aforementioned off-label uses to achieve an appropriate balance between safety and efficacy. In our study specifically, subjects will be instructed to take 81 mg aspirin daily from the initiation of chemotherapy to the time of their interval debulking surgery, which encompasses the duration of the primary NACT treatment course.

7.3 Rationale for Correlative Studies

Not applicable.

7.4 Definition of Evaluable Subjects, On Study, and End of Study

Evaluable subjects are participants who are enrolled in the study, given the study drug (aspirin) and receiving NACT until interval debulking surgery.

On study participants are those who are receiving aspirin or who are censored due to VTE or AE but for whom clinical data is still being collected.

End of study is defined as one year from the investigation start date.

7.5 Early Study Termination

This study can be terminated at any time for any reason by the PI-sponsor. If this occurs, all subjects on study should be notified as soon as possible. Additional procedures and/or follow up should occur in accordance with Section 10.6, which describes procedures and process for prematurely withdrawn patients.

8 STUDY DRUG

8.1 Names, Classification, and Mechanism of Action

Aspirin is a nonsteroidal anti-inflammatory drug (NSAID) that irreversibly inhibits cyclooxygenase-1 and 2. This activity results in a reduction in platelet aggregation (antiplatelet).

8.2 Packaging and Labeling

Medication will be packaged by the Duke Pharmacy Stockroom. The study team will place a 30-day supply of aspirin in labeled, childproof medication vials provided by the Duke bulk pharmacy. Label information will include: patient name, date of birth, medical record numbers, medication dose, and instructions.

8.3 Supply, Receipt, and Storage

Aspirin will be purchased from the Duke Pharmacy Stockroom and placed in labeled, childproof vials for participant distribution. Trained key personnel will maintain responsibility for study drug storage, inventory and distribution. Study drug (ASA) will be securely stored in locked Duke GYN-ONC Office, White Zone, in a locked cabinet with key in custody of GYN ONC CRC.

8.4 Dispensing and Preparation

Study personnel will dispense study drug in Duke GYN ONC Clinics, outpatient settings. If, for some reason, the patient does not receive the drug in person, the same dispensing protocol will be followed but the drug will instead be mailed to the subject's home. The research team will confirm receipt of the study drug.

8.5 Compliance and Accountability

Subjects will complete medication adherence diaries and AE symptom questionnaires that will be reviewed by the research team at subsequent clinic visits (prior to initiation of each cycle of chemotherapy) and will be input into the REDCap database CRF.

8.6 Disposal and Destruction

The study team will destroy unused study drug at the end of the study.

9 SUBJECT ELIGIBILITY

9.1 Inclusion Criteria

- Khorana score = 1
- Over age 18
- English-speaking female patients
- Able to consent
- Recruited from the Duke Gynecology Oncology clinics or Sarasota Memorial Healthcare System
- Receiving neoadjuvant chemotherapy for advanced epithelial ovarian cancer (including primaries of ovarian, Mullerian, fallopian tube, or peritoneal origin)

9.2 Exclusion Criteria

- Allergy or intolerance to study medication
- Indication for a specific form of non-aspirin antiplatelet (i.e. cardiac stent)
- Already on alternative form of anticoagulation
- Active bleeding
- High risk for active bleeding (i.e. recent intracranial bleed or gastrointestinal bleed, known brain metastases)
- Thrombocytopenia (platelet count < 50,000)
- Unable to complete medication adherence diary
- Unable to take oral medications

10 TRIAL PROCEDURES AND ASSESSMENTS

Eligible participants will be recruited from patients with advanced epithelial ovarian cancer (including primaries of ovarian, Mullerian, fallopian tube, or peritoneal origin) who are initiating NACT at the Duke Gynecology Oncology clinics at the Duke Cancer Center and Macon Pond location (Duke Women's Cancer Care Raleigh) or at Sarasota Memorial Healthcare System. A provider will approach the patient and inquire about interest in participating in the study. If the patient desires to receive more information, clinical research personnel will discuss the study with the patient and obtain informed consent if all selection criteria are met (detailed in a prior section). If the patient consents, they will then be considered an enrolled study subject. Electronic consent will be performed in REDcap. Following enrollment in the study, basic demographic information for each patient will be recorded in a secure REDCap database. The initial medical history and physical examination will be conducted per standard of care by the patient's provider at the clinic visit.

Patients will be enrolled and will receive aspirin at the Macon Pond location. All study activities will be performed by the study coordinators, so we do not anticipate needing assistance from the Duke Raleigh study team.

An estimated 120 patients will receive neoadjuvant chemotherapy for advanced ovarian cancer at Duke Gynecology Oncology clinics for the designated study recruitment period of 09/01/2020 to 12/30/2021 with an estimated 50% accrual rate for a total of 60 enrolled patients. Sarasota Memorial Health Care System has been added as an additional site and plans to recruit an additional 60 subjects.

Once enrolled in the study, subjects will receive a 30-day supply of low dose aspirin from the research team and will be instructed to start taking one 81 mg tablet daily starting the first day of their first NACT cycle. Subjects may also be consented after the first day of their first cycle so long as they are taking the aspirin by the end of the day of their second cycle. Subjects will continue taking aspirin until the day of their interval debulking surgery unless previously on low dose aspirin for an alternative indication, in which case they will continue as directed by the prescribing physician. Patients will be instructed to complete medication adherence diaries and AE symptom questionnaires. At each subsequent clinic visit for consideration of an additional NACT cycle, a member of the research team will review medication adherence diaries and AE symptom questionnaires. If symptoms are concerning for a potential AE, the research team personnel will inquire further and discuss with the PI. Please see subsequent sections related to AE monitoring and reporting. No additional components of history and physical exam will be completed outside standard of care performed by the patient's provider prior to initiation of an additional cycle of NACT. Different patients may receive different numbers of cycles, and thus the 30-day supply of aspirin will be re-filled when the decision is made to proceed with an additional cycle.

This study will not impact standard of care treatment. The incidence of venous thromboembolism will be calculated from the study population and compared with a historical control. The incidence of adverse drug events will also be monitored and reported as detailed in a subsequent section.

Subjects will be followed as described above from the initiation of NACT and enrollment through interval debulking surgery unless they withdraw. There will be no additional monitoring in this follow up period with the exception of standard of care evaluation and documentation of the primary outcomes, including adverse drug events.

An outline of the trial procedures and assessments is detailed below:

	Treatment initiation						End of Study
--	----------------------	--	--	--	--	--	--------------

Phase	Screening	Cycle 1	Cycle 2	Cycle 3	Cycle 4	Cycle 5	Cycle 6	Follow-up (interval debulking surgery or completion of NACT)
Obtain Informed Consent	X							
Vital Signs	X	X	X	X	X	X	X	X
Height	X	X						
Weight, BP, Pulse	X	X	X	X	X	X	X	X
Laboratory Assessments (per standard of care)	X	X	X	X	X	X	X	X
Adverse Events		X	X	X	X	X	X	X
Medication Adherence Diary		X	X	X	X	X	X	X
Voils DOSE- Nonadherence measure		X	X	X	X	X	X	X
Provision of additional 30- day supply of study drug		X	X	X	X	X	X	

10.1 Screening Examination

Not applicable

10.2 Treatment Period

Subjects will be instructed to take one 81 mg tablet aspirin daily per study protocol from the time of initiation of NACT through the day of their interval debulking surgery.

10.3 End of Treatment

End of treatment is defined as the day of the subject's interval debulking surgery or, if the patient is not undergoing surgery, 1 week following the last cycle of NACT.

10.4 Follow-up Period

Patients will be followed from initiation of NACT through interval debulking surgery without any additional follow up period.

10.5 End of Study

End of study is defined as one year following initiation of study. We do not anticipate loss to follow up given the association between the study intervention and receipt of neoadjuvant chemotherapy. Participants will be censored at the time of VTE diagnosis or if aspirin is discontinued due to clinically significant AE. In the event

of censorship, data will continue to be collected by the study team until the predetermined follow up period is complete (interval debulking surgery or following completion of NACT, if no surgery).

10.6 Early Withdrawal of Subject(s)

6.6.1. Criteria for Early Withdrawal

Subjects may voluntarily withdraw from the study at any time. The PI may also withdraw a subject from the study at any time based on his/her discretion. Reasons for PI-initiated withdrawal may include, but is not limited to the following:

- Khorana score greater than 1
- Adverse events
- Abnormal laboratory values
- Abnormal test procedure results
- Protocol deviation
- Administrative issues
- Disease progression
- Pregnancy

6.6.2. Follow-up Requirements for Early Withdrawal

When subjects withdraw from the study, whether voluntarily or due to adverse drug events, they will continue to receive standard of care treatment at the discretion of their Gynecology Oncology provider and will continue to be followed accordingly. Since no other method of thromboprophylaxis is routinely implemented during NACT for ovarian cancer, subjects will not receive any other regimen. If subjects withdraw voluntarily, no additional follow up will be required. If subjects are withdrawn due to VTE occurrence of clinically significant AE, the study team will continue to collect clinical data until the predetermined follow up period is complete (interval debulking surgery or following completion of NACT, if no surgery).

6.6.3. Replacement of Early Withdrawal(s)

Subjects who prematurely withdraw from the study will not be replaced.

10.7 Study Assessments

6.7.1. Medical History

Medical history assessments will be conducted at the discretion of the provider per standard of care at clinic visits prior to the initiation of each cycle of chemotherapy. Questionnaires related to assessment of adverse drug events will be administered to subjects at these visits. If there is concern for AEs, a member of the research team will ask additional history to further delineate these events, but no additional medical history will be obtained outside of these requirements.

6.7.2. Physical Exam

Physical examination will be conducted at the discretion of the provider per standard of care at clinic visits prior to the initiation of each cycle of chemotherapy. No additional physical examination components will be required by the study team beyond what is routinely included in clinic visits.

6.7.3. Subject-Rated Measures at Clinic Visits and/or in Daily Diaries

Subjects will be asked to complete medication adherence diaries with each cycle of chemotherapy that will be evaluated by the research team. Data from these diaries will be added to the REDCap database. An example is included in the appendix section 16. Medication adherence diaries will also include a section in which subjects can detail symptoms or adverse events that may be related to use of the study drug. These will be reviewed by a member of the study team at each clinic visit and additional inquiries made, if applicable, when the subject is seen by a member of the study team. At each clinic visit, subjects will also complete the Voils DOSE-Nonadherence questionnaire to evaluate medication adherence.

11 SAFETY MONITORING AND REPORTING

The PI is responsible for the identification and documentation of adverse events and serious adverse events, as defined below. At each study visit, the PI or designee must assess, through non-suggestive inquiries of the subject or evaluation of study assessments, whether an AE or SAE has occurred.

11.1 Adverse Events

An adverse event (AE) is any untoward medical occurrence in a subject receiving study therapy and which does not necessarily have a causal relationship with this treatment. For this protocol, the definition of AE also includes worsening of any pre-existing medical condition. An AE can therefore be any unfavorable and unintended or worsening sign (including an abnormal laboratory finding), symptom, or disease temporally associated with the use of study therapy, whether or not related to use of the study therapy. Abnormal laboratory findings without clinical significance (based on the PI's judgment) should not be recorded as AEs. But laboratory value changes that require therapy or adjustment in prior therapy are considered adverse events.

From the time the subject signs the informed consent form through the End of Study visit (as defined in Section 10.3), all AEs must be recorded in the subject medical record and adverse events case report form.

AEs will be assessed according to the CTCAE version 4.0. If CTCAE grading does not exist for an AE, the severity of the AE will be graded as mild (1), moderate (2), severe (3), life-threatening (4), or fatal (5).

Attribution of AEs will be indicated as follows:

- Definite: The AE is clearly related to the study therapy
- Probably: The AE is likely related to the study therapy
- Possible: The AE may be related to the study therapy
- Unlikely: The AE is doubtfully related to the study therapy
- Unrelated: The AE is clearly NOT related to the study therapy

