5.2 Study Drug

Aspirin is a nonsteroidal anti-inflammatory drug (NSAID) that irreversibly inhibits cyclooxygenase-1 and 2. This activity results in a reduction in platelet aggregation (antiplatelet), which is the rationale for use as an agent for thromboprophylaxis among high risk patients.

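### Bleeding after the day of interval debulking surgery is not collected, and the adverse-event cut-off and last-dose wording are inconsistent

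*Combined protocol and SAP*

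**What the plan says.** Section 11.1 starts adverse-event recording at consent and ends it by cross-reference: "through the End of Study visit (as defined in Section 10.3), all AEs must be recorded". The section it points to is headed End of Treatment and reads "End of treatment is defined as the day of the subject's interval debulking surgery", or 1 week after the last cycle for women who do not have surgery.

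Section 10.4 closes follow-up at the same point: "Patients will be followed from initiation of NACT through interval debulking surgery without any additional follow up period". Section 3.5 ends participation on the day of surgery or at completion of chemotherapy. In the Section 10 schedule the last column is surgery or completion of chemotherapy, and adverse events are marked in it.

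Sections 7.4 and 10.5 use end of study in a different sense, as one year from the start of the study.

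On the last dose, Section 10.2 has aspirin taken "from the time of initiation of NACT through the day of their interval debulking surgery". Section 10 says "Subjects will continue taking aspirin until the day of their interval debulking surgery", with an exception for women already on aspirin for another reason, who follow their prescriber. Section 7.1 also uses *until*, and Section 7.2 says *to the time of* surgery.

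Section 5.2 says the drug "irreversibly inhibits cyclooxygenase-1 and 2". The list of adverse events of special interest under Section 11.1 counts as major any bleed with a haemoglobin fall of at least 2 g/dL or a transfusion of at least 2 units.

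**The concern.** Safety is a primary objective (Sections 3.1 and 6), and the primary safety outcome is the incidence of clinically significant adverse drug events (Section 13.4). The drug is an antiplatelet agent that one section continues through the day of a major operation. The protocol's account of its action gives no reason to assume that the effect ends with the last tablet. Even so, recording closes that same day.

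A report that low dose aspirin was safe in this setting would therefore say nothing about bleeding from the first postoperative day on, and a reader might not notice the gap. The three-monthly review of adverse events cannot detect events that are never collected.

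Separately, staff cannot tell from the text whether a tablet is taken on the day of surgery. Nor is it clear which of two meanings of end of study governs the adverse-event form.

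**Working it through.** The point rests on no sample size, power or event figure, so there is no plan figure to reproduce. The check sets the passages side by side. Call the day of surgery day 0.

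**Step 1: where recording stops**

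| Source | What it fixes | End point for a surgical patient |
|---|---|---|
| 11.1 | Adverse-event recording | The visit referred to 10.3 |
| 10.3 | End of treatment | Day 0 |
| 10.4 | Follow-up | Day 0, nothing further |
| 3.5 | Participation | Day 0 |
| Schedule in 10 | Last adverse-event assessment | Surgery column |
| 7.4, 10.5 | End of study | One year from study start |

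Five of the six entries agree on day 0.

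**Step 2: can the one-year definition supply a later cut-off?** It is a date for the whole study, not a visit for a participant. Taking the target start of 1 September 2020 (Section 13.4), one year ends on 1 September 2021, while enrolment runs to 30 December 2021. The last women would enter about four months after that date, so it cannot serve as their cut-off. For women operated on early it would imply months of recording after surgery, which Section 10.4 rules out.

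**Step 3: does any other passage collect later bleeding?**
- Section 10 says "There will be no additional monitoring in this follow up period with the exception of standard of care evaluation" and documentation of the primary outcomes, but the period it describes ends at surgery.
- The continued data collection for censored women (Section 10.5, and the missing-data paragraph of Section 13.4) runs only to surgery or completion of chemotherapy.
- Section 11.2 on serious events sets no window of its own.

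None of these reaches day 1.

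**Step 4: what is in and what is out**

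| Bleeding | Recorded? |
|---|---|
| Consent to the day before surgery | Yes |
| During surgery and later on day 0 | Yes: 11.1 runs through that day and the schedule marks the surgery column |
| Day 1 onward | No |

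**Step 5: days of recording after the last dose** (last recording day minus last dose day)
- Last dose on day 0 (Section 10.2): 0 − 0 = 0 days.
- Last dose on day −1 (*until* in Sections 7.1 and 10, read as excluding the day of surgery): 0 − (−1) = 1 day.
- Prior aspirin users who continue as prescribed: they may be taking aspirin while nothing is recorded.

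**Step 6: size.** The only bleeding rates in the documents are 0.5% for major bleeding and 0.52% at 90 days (Sections 5.2.2 and 3.1.2). Both come from hip or knee replacement. There is no rate for debulking surgery, no split of surgical bleeding by day, and no figure for how many women will have surgery. The number of events falling on day 1 or later cannot be calculated.

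**The case against.** The best defence is that the trial asks about aspirin during neoadjuvant chemotherapy. The efficacy endpoint is confined to that period, and the safety outcome concerns adverse drug events. Debulking surgery causes blood loss of its own, and in a single arm a haemoglobin fall of 2 g/dL after it cannot readily be put down to aspirin. Pooling such events could swamp the estimate.

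The attribution argument stands, and it is why the two periods should be reported apart. It does not justify leaving the later events uncollected when the drug may be taken up to and including that day. Nor does it touch the inconsistent cut-off and last-dose wording.

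Two stronger readings are tempting, and the documents support neither.
- A reader might infer that surgical bleeding on aspirin is mostly lost. The window includes the day of surgery, so intraoperative and same-day bleeding must be recorded, and nothing shows what share comes later.
- A reader might apply the 0.5% rate to the planned 60 + 60 = 120 women, get 120 × 0.005 = 0.6 expected events before surgery, and set that against a much larger assumed surgical count. But 0.5% is a rate after joint replacement, not one for the chemotherapy period, and any rate for debulking would be invented. The documents also do not say when bleeding on aspirin is most likely.

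**Conclusion.** The point holds in a limited form. As written, the primary safety outcome omits all bleeding from postoperative day 1 in women who have interval debulking surgery, with 0 days of recording after the last dose on the wording of Section 10.2. This follows from the text alone and assumes only that the cross-reference in Section 11.1 means what it says, which Sections 10.4 and 3.5 and the schedule bear out.

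Two drafting conflicts stand beside it. Section 11.1 names an end-of-study visit but points to end of treatment, while Sections 7.4 and 10.5 define end of study otherwise. The last dose is worded in three ways, which leaves a tablet on the day of surgery uncertain.

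No count of missed events can be given. The change should be made because it is cheap and the outcome is primary, not because a large number of events has been shown to be lost.

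**What to change.** 1. In Sections 11.1 and 10.4, extend collection of bleeding events of special interest, taken from the chart, to the routine postoperative visit. The sponsor sets the length of the window.
2. In Section 13.4, report bleeding before surgery separately from perioperative and postoperative bleeding, and state that surgical blood loss cannot be attributed to aspirin in a single-arm study.
3. Correct the cross-reference in Section 11.1 and reconcile it with Sections 7.4, 10.3 and 10.5, so that each participant has one stated adverse-event cut-off relative to the last dose and to surgery.
4. Reconcile the last-dose wording in Sections 7.1, 7.2, 10 and 10.2. Which wording applies is for the sponsor to decide.

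The cost is a short amendment and some chart review per surgical patient, with no added visits. The reported bleeding rate may look less favourable.
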